4.4.3 Treatment Details: All Subsequent Cycles

Trametinib: PO daily

Days: 1-28

Age-based Dosing:

< 6 years of age = 0.032 mg/kg/dose (Maximum dose = 2 mg/day)

NOTE: All patients less than 26.6 kg must receive oral solution. Patients ≥ 26.6 kg may receive oral solution **OR** tablets; however, tablets are preferred if possible.

≥ 6 years of age = 0.025 mg/kg/dose (Maximum dose = 2 mg/day)

NOTE: All patients less than 35 kg must receive oral solution. Patients ≥ 35 kg may receive oral solution **OR** tablets; however, tablets are preferred if possible.

Trametinib should be taken by mouth on an empty stomach, at least 1 hour before or 2 hours after a meal. Nasogastric or G-tube administration of trametinib oral solution is permitted. Do not take a missed dose of trametinib within 12 hours of the next scheduled dose. If vomiting occurs after taking oral solution formulation, the dose should NOT be repeated and the next dose should be administered at the regularly scheduled time. If vomiting occurs within 30 minutes of taking the tablet formulation, the dose of trametinib can be repeated once.

See [Appendix II](#) for [tablet formulation](#) dosing nomogram. Doses of tablet formulation should be rounded to the nearest 0.5 mg.

Trametinib is available as **0.05 mg/mL** reconstituted oral solution. Doses of trametinib oral solution should be rounded to the nearest 0.1 mL (0.005 mg) for doses ≤ 0.11 mg (in oral syringes ≤ 3 mL), to the nearest 0.2 mL (0.01 mg) for doses > 0.11 mg (in oral syringes 5-10 mL volume), and to the nearest 1 mL (0.05 mg) for doses > 0.375 mg. Since trametinib is a hazardous agent, it is recommended that oral dosing syringes should be filled up to 75% of the maximum volume.

Trametinib is distributed by CTEP, DCTD, NCI. **Do not use commercial supply.**

See [Section 5.0](#) for **Dose Modifications based on Toxicities.**

Complete the end of cycle disease evaluations within three days of the last dose of trametinib on Day 28.

Following completion of the cycle, the next cycle starts on Day 29 or when starting criteria are met (see [Section 3.2.5](#)), whichever occurs later. Please continue onto the next cycle no later than 14 days from the end of the previous cycle. Results of the JMML mutant allele burden test collected at the end of odd numbered cycle are not required to proceed to the next cycle.

5.0 DEFINITIONS AND DOSE MODIFICATION FOR TOXICITY

All dose modifications should be based on the worst preceding toxicity.

5.1 Definition of Dose-Limiting Toxicity (DLT)

DLT will be defined as any of the following events that are possibly, probably or definitely attributable to trametinib.

Dose limiting hematological and non-hematological toxicities are defined differently.

5.1.2 Hematological dose limiting toxicity

- a) Hematologic DLT will be defined as failure to recover a peripheral ANC > 500/ μ L and platelets > 20,000/ μ L by 42 days after the first treatment day, not due to malignant infiltration.

Note: Grade 4 febrile neutropenia will not be considered a dose-limiting toxicity.

5.2 Dose Modifications for Hematological Toxicity

There are no modifications for patients with persistent JMML who have never experienced recovery of normal hematologic parameters. If a patient does have recovery of normal hematologic parameters and then experiences Grade 4 neutropenia or Grade 4 thrombocytopenia, the treatment will be held. Counts should be checked twice weekly during this time. If the toxicity resolves to peripheral absolute neutrophil count (ANC) \geq 1000/ μ L and platelet count \geq 75,000/ μ L within 14 days of drug discontinuation, the patient may resume treatment with 25% dose reduction in patients receiving oral solution or the specified dose reduction in patients receiving tablets (See [Appendix II](#)). Doses reduced for toxicity will not be re-escalated, even if there is minimal or no toxicity with the reduced dose.

If toxicity does not resolve to peripheral absolute neutrophil count (ANC) \geq 1000/ μ L and platelet count \geq 75,000/ μ L within 14 days of drug discontinuation, the patient must be removed from protocol therapy.

If dose-limiting toxicity recurs in a patient who has resumed treatment at the reduced dose, the patient must be removed from protocol therapy.

5.3 Dose Modifications for Non-Hematological Toxicity

If a patient experiences non-hematological dose-limiting toxicity as defined in [Section 5.1.1](#), the treatment will be held. When the toxicity resolves to meet eligibility parameters or baseline within 14 days of drug discontinuation, the patient may resume treatment with 25% dose reduction in patients receiving oral solution or the specified dose reduction in patients receiving tablets (See [Appendix II](#)). Doses reduced for toxicity will not be re-escalated, even if there is minimal or no toxicity with the reduced dose.

If toxicity does not resolve to meet eligibility or baseline parameters within 14 days of drug discontinuation, the patient must be removed from protocol therapy.

If any dose-limiting toxicity recurs in a patient who has resumed treatment at the reduced dose level, the patient must be removed from protocol therapy.

5.4 Guidelines and Dose Modifications for Trametinib Events of Special Interest

Dose modification and adverse event (AE) guidelines are outlined in the sections below for AEs that are deemed possibly related to trametinib:

- AEs not otherwise specified
- Rash
- Visual changes
- Diarrhea
- Liver chemistry elevation

- Ejection fraction changes
- Hypertension
- Prolonged QTc
- Pneumonitis

5.4.1 Trametinib Dose Modification for Toxicities Not Specified in Subsequent Sections:

Trametinib Treatment Modification for Clinically Significant Toxicities Deemed Related to Trametinib (This section is not for specific AEs such as hypertension, rash, ejection fraction changes, pneumonitis, diarrhea, liver chemistry, QTc prolongation, or visual changes. Refer to other sections for these specific AEs).	
CTCAE v5 Grade	Dose Modification
Grade 1 and tolerable Grade 2	
 • Continue trametinib at current dose level • Monitor closely • Provide supportive care according to institutional standards
Intolerable Grade 2 and Grade 3	
 • Interrupt treatment until resolution to Grade 1 or baseline • Upon resolution to baseline or Grade 1, restart with 25% dose reduction in patients receiving oral solution or the specified dose reduction in patients receiving tablets (See Appendix II) • If the intolerable Grade 2 or Grade 3 toxicity recurs, permanently discontinue trametinib
Grade 4	
 • Interrupt treatment • Monitor closely • Provide supportive care according to institutional standards • If event resolves to Grade 1 or baseline discuss potential continuation of trametinib with study chair; if continuation of treatment agreed, then restart trametinib with 25% dose reduction in patients receiving oral solution or at specified dose reduction in patients receiving tablets (See Appendix II) • If event does not resolve, permanently discontinue trametinib

5.4.2 Trametinib Dose Modifications for Rash:

Dermatologic complications are frequent adverse events in subjects receiving trametinib and a proactive approach should be taken. All subjects should avoid unnecessary sunlight and use sunscreen whenever there is possible exposure. See [Section 4.1.5](#) for prophylactic treatment for prevention of dermatologic toxicity

Reactive Management:

It is strongly recommended that subjects who develop rash/skin toxicities receive evaluations by a dermatologist for management of the specific side effect.

For pruritic lesions, the use of cool compresses and oral antihistamine agents may be helpful.

For fissuring, the use of Monsel's solution, silver nitrate or zinc oxide cream is advised.

For desquamation, thick emollients and mild soap are recommended.

For paronychia, antiseptic bath and local potent corticosteroids in addition to oral antibiotics are recommended, and if no improvement is seen, a dermatology or surgery consultation is recommended.

For infected lesions, bacterial and fungal culturing followed by the appropriate culture-driven systemic or topical antibiotics is indicated.

Management and Trametinib Dose Modification for Rash		
Event CTCAE Grade	Management Guideline	Action and Dose Modification
Grade 1	Initiate prophylactic and symptomatic treatment measures. ^a Use moderate strength topical steroid. ^b Reassess after 2 weeks.	Continue trametinib.
Grade 2	Initiate prophylactic and symptomatic treatment measures. ^a Use moderate strength topical steroid. ^b Reassess after 2 weeks.	Continue trametinib If rash does not recover to ≤ Grade 1 within 2 weeks, interrupt trametinib until recovery to ≤ Grade 1, restart trametinib at reduced dose (25% dose reduction in patients receiving oral solution or at specified dose reduction in patients receiving tablets (See Appendix II))
Grade ≥3	Use moderate strength topical steroids ^b (PLUS) methylprednisolone dose pack. Consult dermatologist.	Interrupt trametinib until rash recovers to Grade ≤1. Restart with trametinib at reduced dose (25% dose reduction in patients receiving oral solution or at specified dose reduction in patients receiving tablets (See Appendix II)) If no recovery to Grade ≤ 2 within 2 weeks, permanently discontinue trametinib.

a. Rash prophylaxis is recommended for the first 6 weeks of study treatment

b. Moderate-strength topical steroids hydrocortisone 2.5% cream or fluticasone propionate 0.5% cream

c. Notify the study chair.

5.4.3 Trametinib Dose Modifications for Visual Changes (Eye Disorders)

Trametinib is known to be associated with visual adverse events. An age-appropriate ophthalmologic examination should be performed by an ophthalmologist (without sedation) at screening, may be performed without dilation at discretion of ophthalmologist and can be accomplished using imaging with a non-mydratic fundus camera. During the study, ophthalmologic exams will be repeated by an ophthalmologist at the end of cycle 1 and every 12 weeks thereafter. If the child or parent report visual problems they will be referred promptly for an ophthalmology assessment.

If visual changes are clearly unrelated to study treatment (e.g., allergic conjunctivitis), then monitor closely as it may be reasonable to defer ophthalmic examination. Special attention will be given to retinal findings (e.g., retinal pigment epithelial detachment (RPED) or retinovascular abnormalities (i.e., branch or central retinal vein occlusions [RVO])). For subjects with clinical suspicion of RPED or RVO, fundus photography, and optical coherence tomography will be performed.

The ophthalmology exam can include best corrected visual acuity, visual field examination, tonometry, slit lamp biomicroscopic examination, and indirect ophthalmoscopy as indicated. Optical coherence tomography will be performed if retinal abnormalities are suspected. Other types of ancillary testing including visual field examination, fundus photography, and fluorescein angiography may also be indicated as determined by clinical exam.

Guidelines regarding event management and dose reduction for visual changes considered to be related to study treatment are provided in the table below.

Management and Trametinib Dose Modification for Visual Changes and/or Ophthalmic Examination Findings		
Event CTCAE Grade	Management Guideline	Dose Modification
Asymptomatic; clinical or diagnostic observations only *	
 Consult ophthalmologist within 7 days of onset. 	
 If dilated fundus examination cannot be performed within 7 days of onset, hold trametinib until RPED and RVO can be excluded by retina specialist/ophthalmologist. If RPED and RVO excluded, continue/or restart trametinib at same dose. If RPED suspected/diagnosed: See RPED dose modification table below (following this table); report as SAE. If RVO diagnosed: Permanently discontinue trametinib and report as SAE.
Symptomatic with mild to moderate decrease in visual acuity; limiting instrumental ADL	
 Consult ophthalmologist immediately. 	
 Hold trametinib If RPED or RVO excluded, restart trametinib at same dose. If RPED diagnosed: See RPED dose modification table below; report as SAE. If RVO: Permanently discontinue trametinib and report as SAE.
Sight-threatening consequences; urgent intervention indicated; best corrected visual acuity of 20/200 or worse in the affected eye	
 Consult ophthalmologist immediately. Report as SAE. 	
 Hold Trametinib If RPED/RVO excluded, may restart trametinib at same or reduced dose after discussion with the study chair. If RVO or RPED, permanently discontinue trametinib.

Management and Trametinib Dose Modification for Visual Changes and/or Ophthalmic Examination Findings		
Event CTCAE Grade	Management Guideline	Dose Modification
Abbreviations: RPED = retinal pigment epithelial detachments; RVO = retinal vein occlusion; SAE = serious adverse event		
*If visual changes are clearly unrelated to study treatment (e.g., allergic conjunctivitis), monitor closely but ophthalmic examination is not required.		

Trametinib Dose Modification for RPED	
Event CTCAE Grade	Action and Dose Modification
RPED (Asymptomatic; clinical or diagnostic observations only)	
 Continue treatment with retinal evaluation monthly until resolution. If RPED worsens, follow instructions below.
RPED (Symptomatic with mild to moderate decrease in visual acuity; limiting instrumental ADL)	
 Interrupt trametinib. Retinal evaluation monthly. If improved to \leq Grade 1, restart trametinib with a reduced dose (25% dose reduction in patients receiving oral solution or at specified dose reduction in patients receiving tablets (See Appendix II)) If no recovery within 4 weeks permanently discontinue trametinib

5.4.4. Trametinib Dose Modification for Diarrhea

Etiology and attribution. Consider evaluation for an alternative etiology of diarrhea as clinically indicated. These include medications (e.g., stool softeners, laxatives, antacids, etc.), infection by *C. difficile*, partial bowel obstruction, malabsorption/lactose intolerance, fecal impaction, or diets high in fiber or lactose.

For Grade \leq 2 diarrhea:

Dietary modifications may include: stop all lactose-containing products and eat small meals. A bananas, rice, apples, toast (BRAT) diet can be helpful.

Encourage oral hydration according to institutional weight oral hydration guidelines as clinically appropriate.

For all subjects consider administration of loperamide (Table 5.4.4.1) with dosing per institutional guidelines or as suggested below. Continuation of loperamide is suggested until the subject is diarrhea-free for at least 12 hr.

If diarrhea resolves to Grade \leq 1 within 72 hr of anti-diarrheal measures or supportive care measures, continue study treatment without interruption or dose reduction.

If Grade 2 diarrhea persists after 72 hr total treatment with loperamide or supportive measures in children $<$ 2 years, hold study treatment and consider start of second-line agents (octreotide) as clinically indicated. If diarrhea resolves to Grade \leq 1 or baseline within 7 days resume study treatment with dose reduction. If Grade $>$ 2 diarrhea does not resolve in \leq 7 days without study treatment, discontinue protocol therapy.

Table 5.4.4.1 Loperamide Dosing

Age	Weight (kg)	Initial Dose (start after first loose bowel movement)	Subsequent Doses	Maximum daily dose
> 1 mo to ≤ 12 years	<13	0.5 mg	0.5 mg every 3 hr while awake, every 4 hr during sleep	4 mg/day
	13 to <20	1 mg	1 mg every 4 hr	6 mg/day
	20 to <30	2 mg	1 mg every 3 hr while awake, every 4 hr during sleep	8 mg/day
	30 to <43	2 mg	1 mg every 2 hr while awake, every 4 hr during sleep	12 mg/day
≥ 13 years	≥ 43	4 mg	2 mg every 2 hr while awake, every 4 hr during sleep	16 mg/day

For Grade 3 or 4 diarrhea:

Hold study treatment until symptoms resolve to ≤ Grade 1 or baseline then may resume study treatment with a dose reduction (25% dose reduction in patients receiving oral solution or specified dose reduction in patients receiving tablets (See [Appendix II](#)).

If loperamide has not been initiated, initiate loperamide immediately using institutional or protocol guidelines for dosing.

For dehydration, use intravenous fluids as appropriate; if severe dehydration, consider administration of octreotide.

5.4.5. Trametinib Dose Modification for Liver Chemistry Changes:

Liver chemistry threshold stopping criteria have been designed to assure subject safety and to evaluate liver event etiology during administration of study treatment(s) and the follow-up period. Upper limit of normal (ULN) for ALT in this study will be 45 U/L and ULN for AST is 50 U/L. Adverse event grades will be based on increases above the upper limit of normal, regardless of the subject's baseline. See [Appendix X](#) for toxicity grading table. Study treatment(s) will be stopped if any of the following liver chemistry stopping criteria is/are met:

1. ALT ≥3 times upper limit of normal (ULN) and bilirubin ≥2 times ULN (or ALT ≥3 times ULN and international normalization ratio [INR] >1.5)

i. NOTE: Serum bilirubin fractionation should be performed if testing is available. If fractionation is unavailable, urinary bilirubin is to be measured via dipstick (a measurement of direct bilirubin, which would suggest liver injury).

2. ALT ≥5 times ULN.

3. ALT ≥3 times ULN if associated with the appearance or worsening of rash or hepatitis symptoms (fatigue, nausea, vomiting, right upper quadrant pain or tenderness, or jaundice) or hypersensitivity (such as fever, rash or eosinophilia).

4. ALT ≥ 3 times ULN persists for ≥ 4 weeks.

5. ALT ≥ 3 times ULN and cannot be monitored weekly for 4 weeks.

Subjects with ALT ≥ 3 times ULN and < 5 times ULN and bilirubin < 2 times ULN, who do not exhibit hepatitis symptoms or rash, can continue study treatment(s) as long as they can be monitored weekly for 4 weeks. See following section for details on weekly follow-up procedures for these subjects.

5.4.5.1. Liver Chemistry Follow-up Procedures

The procedures listed below are to be followed if a subject meets the liver chemistry stopping criteria 1 through 5 defined in Section 5.4.5:

- Immediately discontinue study treatment.
- Notify the study chair within 24 hr of learning of the abnormality to confirm the subject's study treatment(s) cessation and follow-up.
- Complete the "Safety Follow-Up Procedures" listed below.
- If the event also meets the criteria of a SAE (see [Section 11.2](#)), the SAE data collection tool will be completed separately with the relevant details.
- Upon completion of the safety follow-up permanently withdraw the subject from the study and do not re-challenge with study treatment(s).

Safety Follow-Up Procedures for subjects with ALT ≥ 3 times ULN:

- Monitor subjects weekly until liver chemistries (ALT, aspartate aminotransferase [AST], alkaline phosphatase [ALP], and bilirubin) resolve, stabilize or return to within baseline values.

Safety Follow-Up Procedures for subjects meeting stopping criterion 1 (ALT ≥ 3 times ULN and bilirubin ≥ 2 times ULN [or ALT ≥ 3 times ULN and INR > 1.5]):

- This event is considered an SAE (see [Section 11.2](#)). Serum bilirubin fractionation should be performed if testing is available. If fractionation is unavailable, urinary bilirubin is to be measured via dipstick (a measurement of direct bilirubin, which would suggest liver injury).
- Make every reasonable attempt to have subjects return to the clinic within 24 hr for repeat liver chemistries, additional testing, and close monitoring (with specialist or hepatology consultation recommended).
- Monitor subjects twice weekly until liver chemistries (ALT, AST, ALP, and bilirubin) resolve, stabilize or return to within baseline values.
- In addition, every attempt should be made to carry out the liver event follow-up assessments described in Section 5.4.5.2.

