8.0 CRITERIA FOR REMOVAL FROM PROTOCOL THERAPY AND OFF STUDY CRITERIA

8.1 Criteria for Removal From Protocol Therapy

- a) Progressive disease.
- b) Adverse Events requiring removal from protocol therapy, as stated in [Section 5.0](#).
- c) Patients who receive concurrent anticancer or investigational therapy, as stated in [Section 4.1.4](#).
- d) Refusal of further protocol therapy by patient/parent/guardian.
- e) Completion of 12 cycles of therapy.
- f) Physician determines it is in patient's best interest.
- g) Non-compliance that in the opinion of the investigator does not allow for ongoing participation.
- h) Patients who develop a second malignant neoplasm.

Patients who are removed from protocol therapy (except for 8.1.g) are to be followed until they meet the criteria for Off Study (see below). Follow-up data will be required unless consent was withdrawn.

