9.3 Methods of Analysis

Response criteria are described in [Appendix III](#). A responder is defined as a patient who achieves a best response (as defined in [Section 10.2](#)) of PR or CR on the study prior to having an overall response of PD (as defined in [Section 10.2](#)); all others will be considered non-responders. The evaluation period for determination of the best response will be 12 treatment cycles. Response rates will be calculated as the percent of evaluable patients who are responders, and confidence intervals will be constructed accounting for the two-stage design.

Duration of response (Aim 1.2.5) will be defined as the time from first occurrence of PR or CR until the first occurrence of PD, death, or going off study. Patients who progress will be considered to have had an event, patients who die prior to progressing will be considered to have a competing event, and patients who go off study prior to progressing will be censored at time of last contact. The analysis will be done using the method of Gray.⁴⁵

Toxicity tables will be constructed to summarize the observed incidence by type of toxicity and grade. A patient will be counted only once for a given toxicity for the worst grade of that toxicity reported for that patient. Toxicity information recorded will include the type, severity, time of onset, time of resolution, and the probable association with the study regimen.

The analytic unit for monitoring for protocol-specific toxicities will be the patient-course: Each course where the patient receives the agent and either 1) has a protocol-specific toxicity event, or 2) receives at least 85% of their assigned dose during the cycle will be considered in the analysis. If there is strong evidence (posterior probability of at least 70% with at least 2 observed toxicities) that there is a per course protocol-specific toxicity probability of more than 20%, such information will be presented to the DSMC.

We will use a Bayesian rule to monitor for protocol-specific toxicities. We will assume a beta prior distribution with $\alpha = 0.52$ and $\beta = 2.08$. At least once per month, we will calculate the posterior probability (given the data) that the probability of protocol-specific toxicity exceeds the 20% threshold:

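### The liver stopping rule in Section 5.4.5.1 withdraws patients from the study, while Sections 8.1 and 8.2 keep them in follow-up after removal from therapy

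*Combined protocol and SAP*

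**What the plan says.** Section 5.4.5 lists five liver chemistry criteria and attaches one consequence to them: "Study treatment(s) will be stopped if any of the following liver chemistry stopping criteria is/are met". It says nothing about leaving the study.

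Section 5.4.5.1 sets out what follows. Its scope is all five criteria: "The procedures listed below are to be followed if a subject meets the liver chemistry stopping criteria 1 through 5". The first instruction already ends treatment. The last one adds that, once the safety follow-up is complete, the site is to "permanently withdraw the subject from the study and do not re-challenge with study treatment(s". The safety follow-up that comes before withdrawal is monitoring of liver chemistries until they "resolve, stabilize or return to within baseline values".

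Section 8.1, item b, lists among the reasons for leaving therapy "Adverse Events requiring removal from protocol therapy, as stated in" Section 5.0. Patients removed from therapy, with item g (non-compliance) as the only exception, "are to be followed until they meet the criteria for Off Study", and their follow-up data are required unless consent is withdrawn. Section 8.2 gives six Off Study reasons: death, loss to follow-up, entry into another COG therapeutic study, withdrawal of consent, five years from enrollment, and never having been treated. None is a toxicity.

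Duration of response is secondary aim 1.2.5. For its analysis, Section 9.3 states that "patients who go off study prior to progressing will be censored at time of last contact".

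**The concern.** The two sets of instructions give the same patient two different statuses. Under Section 8, a patient stopped for a liver event is off therapy and still followed. Under the last instruction of 5.4.5.1, that patient leaves the study once the liver chemistries settle. That instruction mentions the study and the study treatment separately, so taking the first to mean the second is not the obvious reading.

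What is at stake is mainly duration of response. A responder withdrawn in this way would be censored because of a treatment toxicity, soon after the drug was stopped. Censoring of that kind is potentially informative: if progression becomes more likely once the drug stops, follow-up ends just as the risk rises, and duration of response would tend to look longer than it is. Section 2.2.1 gives some reason to take this seriously, since in the mouse models mutant cells persisted under MEK inhibition. Later progression (the event) and an unrelated later death (the competing event) would go unrecorded, as would late events that no other rule obliges the site to report.

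**Working it through.** The plan states no figure on this point, so the check is a comparison of text followed by a short calculation of scale.

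**Step 1: the sections side by side.**

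| Question | Sections 5.4.5 and 5.4.5.1 | Sections 8.1 and 8.2 |
|---|---|---|
| What does the liver event end? | 5.4.5: treatment. 5.4.5.1: treatment, then study participation | Protocol therapy (8.1.b) |
| What is followed afterwards? | Liver chemistries until settled, then withdrawal | The patient, until an Off Study reason applies |
| Is toxicity a reason to leave the study? | Yes, for all five liver criteria | No; none of the six reasons |

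Section 5.4.5.1 belongs to Section 5.0, so a liver stop falls under 8.1.b. The only exception to follow-up is 8.1.g. Both instructions therefore apply to the same patient, and they conflict.

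**Step 2: is the liver wording typical of Section 5?** It is not. Sections 5.2 and 5.3 remove the patient from protocol therapy. The rules on rash, visual changes, pneumonitis and ejection fraction discontinue trametinib. The QTc rule discontinues study treatment, the diarrhea rule discontinues protocol therapy, and Grade 4 hypertension takes the patient off protocol therapy. Only the liver rule refers to withdrawal from the study, and no reason is given for shorter follow-up after a liver event.

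**Step 3: route to the analysis.** A responder who meets a liver criterion is stopped, monitored until the chemistries settle, and then withdrawn. Section 9.3 censors such a patient at last contact if withdrawal counts as going off study. If a statistician instead held strictly to the 8.2 list, there would still be no later data, so the patient would in effect be censored at about the same time.

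**Step 4: what would still be captured.** Section 11.3 keeps these reportable: related serious events more than 30 days after the last dose (11.3.1), disabling events at any time after treatment (11.3.2), related deaths beyond 30 days (11.3.3) and secondary malignancies (11.3.4). What is exposed is progression, unrelated deaths beyond 30 days, and late events outside those categories. Reporting also depends on the site learning of an event once scheduled collection has ended.

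**Step 5: scale.** Section 9.2 has 20 patients over two stages and a target response rate of 25%.

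- Expected responders: 0.25 × 20 = 5. One withdrawn responder is 1/5 = 20% of the set.
- With 3 responders, the fewest that would declare the agent effective at Stage 2: 1/3 = 33.3%.
- With 8 responders: 1/8 = 12.5%.

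The documents give no rate for meeting the liver rule. Taking an assumed rate q, independent of response, the chance that at least one of R responders is affected is 1 − (1 − q)^R:

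| Assumed q | R = 3 | R = 5 | R = 8 |
|---|---|---|---|
| 5% | 14.3% | 22.6% | 33.7% |
| 10% | 27.1% | 41.0% | 57.0% |
| 20% | 48.8% | 67.2% | 83.2% |

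The nearest figure in the documents is the 9% rate of Grade 3/4 hepatic toxicity in adults with myeloid malignancies (Section 2.3.1). At q = 9% and R = 5 the result is 1 − 0.91^5 = 1 − 0.624 = 38%. That is only an anchor. It comes from adults, and the rule is not a grade: four of the five criteria can apply from ALT 3 × 45 = 135 U/L when their other conditions are met, whereas Appendix X starts Grade 3 at 226 U/L.

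**The case against.** The strongest reply is that Section 8 is the controlling section. It classes Section 5.0 adverse events as removal from therapy and requires follow-up, and the term on which 9.3 relies, off study, is defined in 8.2 without any toxicity. The liver bullet sits in a dose-modification section whose parent rule only stops treatment. A ban on re-challenge would also be redundant for someone who had truly left the study, so the sentence can be read as an emphatic way of saying permanently off therapy. On that view nothing is lost.

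This stands in part. Sites may well follow Section 8, and Section 8 suggests that nobody meant to drop these patients. But the document does not say which section prevails, and sites that read it differently would follow patients differently. A rule that is harmless only when disregarded still needs correcting.

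The reply is right about size, and a reader might infer more than the documents support:

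- **That 20% of duration-of-response follow-up is lost.** One in five is a share of patients. Response time up to last contact still counts, and only that patient's remaining time is at risk.
- **That up to five years are lost.** Five years from enrollment is a ceiling. Duration of response also ends at progression, death or another Off Study reason. Section 7.1 leaves later data collection to a case report form schedule that is not in the documents.
- **That nothing later would be recorded.** Section 11.3 preserves the categories listed in the working.
- **That the primary result is distorted.** Section 9.4 makes a patient evaluable after one dose, so the denominator does not move. At most, a response not yet documented at withdrawal could be missed, such as the four weeks that Appendix III requires for a clinical complete remission.

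**Conclusion.** The contradiction is real and visible in the text: Section 5.4.5.1 ends study participation for a group of patients whom Sections 8.1 and 8.2 keep in follow-up. Harm follows only where a site applies 5.4.5.1 literally. In that case the censoring of a responder is tied to treatment toxicity and is potentially informative, and progression and unrelated late deaths go unseen.

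The consequence falls on a secondary aim and on late safety, not on the two-stage decision. With so few responders one patient matters: 1 in 5 at the target response rate, 1 in 3 at the smallest positive result. How likely that is cannot be derived from the plan; the probabilities shown rest wholly on assumed rates and on independence from response. The direction of any bias is likewise an inference that depends on whether risk rises after the drug is stopped. It should be corrected, as an inconsistency of wording rather than a flaw in the design.

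**What to change.** Reconcile the follow-up status in Section 5.4.5.1 with Sections 8.1 and 8.2. One way is to replace the words on withdrawal from the study with a statement that the patient is off protocol therapy and that follow-up continues under Section 8. The liver thresholds, the stopping of treatment and the no-re-challenge instruction are outside this point and stay as written.

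If ending follow-up after a liver event was in fact intended, it should be added to Section 8.2 with a reason, and Section 9.3 should say how those patients are handled.

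The cost is one phrase in an amendment. The follow-up itself is already planned for other patients removed from therapy for adverse events, so no new procedure is needed. If any patient has already been withdrawn under the present wording, the report should give the number and say how many were responders.
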